## 9 QUALITY CONTROL AND QUALITY ASSURANCE

## 9.1 Confidentiality and Security

The registry will collect only clinical data and test results. There is a theoretical risk of breach of confidentiality or a data security loss although exhaustive efforts will be made to minimize this inherent risk. All sites must demonstrate proper physical and electronic security measures in order to participate in the registry.

To protect the confidentiality of the participants it is required:

- 1. Separate all direct participant identifiers (i.e., names, social security numbers, medical record numbers, etc.) from outcome information stored in the registry
- 2. Securing in a separate location and limiting access to information linking codes assigned to the registry information with direct participant identifiers
- 3. Limiting access to information contained within the registry to investigators and approved study staff

All data from healthcare providers will be entered into the registry through the eCRF system maintained by Viedoc™. The electronic data capture system is 21 CFR Part 11 compliant. All computers will be used to collect and send data during implementation of the study or to receive or store data at the central location will be password protected. A password will be required to open Windows® and a second, different password will be required to open the electronic data capture system, Viedoc™. This closed system requires a unique identification for each user.

Electronic forms will be stored on a secure dedicated server with appropriate firewalls. The system will use 128- bit encryption (SSL certificate). This technology is the same as that used for online ecommerce applications to protect consumer information such as name, address, and credit card details. The system has a secure login along with audit control mechanisms to meet HIPAA standards. Servers are scanned for viruses and systems are in place to detect attempts at unauthorized entry. The data base server is backed up daily internally. All transactions to the database are stored in archive logs as re-do data and are accessible to enable quick recovery of all data should the need arise. Backup files are written nightly to back up servers. Weekly, a monthly backup copy is stored off-site in perpetuity.

For follow-up beyond 2 years, the ePRO system allows the registry staff to automatically contact the patient for follow-up information. For example, patients can receive an automatic text message or email that opens to a follow-up electronic questionnaire for long-term follow-up. The link to the ePRO also will be embedded in the patient education app that will include content (videos and written information) approved by the steering committee related to FMT indications, preprocedure checklist, potential adverse events, and post-procedure follow-up. The app will be maintained at Sinai AppLab, Icahn School of Medicine at Mount Sinai and will be made available to all FMT patients enrolled in the registry.

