## 3 STUDY DESIGN

## 3.1 Overview Study Design Summery

This registry will prospectively enroll 4,000 patients who undergo FMT at 75 sites throughout North America. Information on FMT methodology employed (e.g., screening of donor and recipient, preparation, FMT delivery) will be collected from each site. The indication for FMT as well as baseline information on recipient will also be collected. Following FMT, patients will be followed at regular intervals up to 10 years post FMT. This will include follow-up information from the patient's healthcare provider at 1 month, 6 months, 1 year, and 2 years after FMT as well as direct communication with patients at least annually up to 10 years after FMT. Follow-up information collected will be designed to assess potential short-term and long-term safety and effectiveness.

Anticipating changes in therapy from current FMT to use of other gut-related microbiota products in coming years, the Registry will be constructed with the flexibility to collect methodological and follow-up clinical information for all forms of gut-related-microbiota products and for a variety of indications besides CDI and IBD.

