## 4.5 Costs and Payments

This is not a clinical treatment study and all costs associated with the care and treatment of patient receiving FMT and follow-up will be paid by the patient or their insurance provider. No costs will be incurred by participants related to participation in the Registry. Continued patient participation will be encouraged with a \$10 gift card for providing health information each year beginning 1 year post-FMT.

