#### **5.1** Data Elements

Data elements that may be collected for the FMT registry are shown in Supplements 1-6. In order to make the data elements as broad and inclusive as possible, the FMT Registry Steering Committee developed the data elements based on current guidelines and published recommendations, their own treatment protocols/experience, and feedback from 15 additional large FMT practice sites. *Supplement 1* details the data elements related to FMT technique including donor and recipient screening. For sites that employ a donor questionnaire, *Supplement 2* provides potential questions used on a questionnaire, based on those used for blood transfusion. *Supplement 3* shows the data elements for baseline characteristics of donors and recipients and for FMT treatment indications, while *Supplement 4* provides effectiveness outcomes data elements. Finally, *Supplements 5* and 6 detail data elements for short-term and long-term safety outcomes. Patients will be followed at regular intervals for up to 10 years after FMT for pre-defined and spontaneously reported adverse events and for pre-defined outcomes of effectiveness. Investigators will enter follow-up data at 1 month, 6 months, 1 year and 2 years post-FMT, and patients will then provide data annually up to 10 years.

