#### 6.1 Adverse Events

Based on numerous case reports and small clinical studies in the literature, it appears that FMT for refractory CDI is generally well-tolerated and safe, although occasional adverse events (e.g., febrile

episodes) have been reported. Importantly, a prospective systematic evaluation of both immediate and short-term predefined adverse outcomes in a large number of patients undergoing FMT is currently lacking. In the absence of any consensus guideline on practice standards for FMT in the U.S. and the lack of regulatory oversight for the treatment of refractory CDI, the committee has learned through polling of sites performing FMT that there is a wide variation in the practice of FMT. This variance in practice also raises potential concerns about risks for both short-term and long-term risks. As discussed in section 5.1, to broadly capture adverse outcomes in recipients of FMT that may be indicative of a safety concern, we have developed two data entry fields: 1) Short-Term Adverse Outcomes (within 30 days)—Supplement 5, and 2) Long-term Adverse Outcomes (up to 2 years reported by the physician and 10 years reported by the patient)—Supplement 6. Adverse event information will be provided by the FMT provider site at four time points post-FMT: 1 month, 6 months, 1 year, and 2 years. In addition, patients will be contacted directly by email and text at least annually for up to 10 years to provide follow-up information via a dedicated portal maintained by the Icahn School of Medicine at Mt. Sinai.

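### Section 5.1 starts scheduled patient reporting after the 2-year provider form while Section 4.5 starts it at year 1; built to 5.1, the two reporters never overlap.

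*Protocol*

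**What the plan says.** Provider reporting is consistent throughout: sites report at months 1 and 6 and at years 1 and 2, and then stop. The start of scheduled patient reporting is not consistent.

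**Statements that make it sequential**
- Protocol Section 5.1 (Data Elements): the investigators' entries are listed first, ending at year 2, and the sentence closes by putting patients after them: "patients will then provide data annually up to 10 years".
- Protocol Section 9.1 (Confidentiality and Security): "For follow-up beyond 2 years, the ePRO system allows the registry staff to automatically contact the patient for follow-up information".

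**Statements that make it parallel**
- Protocol Section 4.5 (Costs and Payments): the gift card is given "for providing health information each year beginning 1 year post-FMT".
- Protocol Section 3.1 (design overview): the provider reports are listed and the text then adds "direct communication with patients at least annually up to 10 years after FMT".
- Protocol Section 6.1 (Adverse Events): after the four provider time points it says, as an addition, that "patients will be contacted directly by email and text at least annually for up to 10 years".

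The title of Supplement 6 sets the long-term windows at 2 years for physician report and 10 years for patient report. It says when each source ends but not when patient reporting begins.

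**The concern.** Long-term safety is part of the primary objective, and Section 2.2.1 treats it as the larger and less certain part. The outcomes in Supplement 6 are mostly new diagnoses: autoimmune, metabolic, cardiovascular, psychiatric and neurologic disease, and cancer. How often such diagnoses are recorded can depend on who is asked. An FMT site may not hear of new hypertension or asthma treated elsewhere; a patient may omit or mislabel a diagnosis that a physician would record.

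If patient reports begin only when provider reports have ended, the reporter changes for every patient at the same point of follow-up. Time since FMT and data source are then fully confounded across year 2. Section 8.3 relies on the prospective cohort to estimate incidence accurately, and any comparison of rates before and after year 2 would rest on the untested assumption that the two sources capture events equally.

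This is a matter of the data-collection schedule, which an analysis plan cannot repair. If scheduled patient reports at years 1 and 2 are not collected, no later method can supply them.

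**Working it through.** The plan states no figure on this point. The check is a comparison of the schedule statements and a count.

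**Inputs**
- Provider time points, in years: 1/12, 1/2, 1, 2 (Sections 3.1, 5.1, 6.1).
- Patient reports: annual, last at year 10 (Sections 3.1, 5.1, 6.1).
- First patient report: year 1 (Section 4.5), or the first annual point after the 2-year provider report, year 3 (Section 5.1 as worded).

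**Count.** Annual patient reports = last year − first year + 1. Shared time points = the years that appear in both lists.

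| Reading | Patient reports at years | Number | Shared with provider |
|---|---|---|---|
| Parallel (4.5, with 3.1 and 6.1) | 1 to 10 | 10 − 1 + 1 = 10 | 2 (years 1 and 2) |
| Sequential (5.1, with some support from 9.1) | 3 to 10 | 10 − 3 + 1 = 8 | 0 |

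The readings differ by 10 − 8 = 2 questionnaires per patient. Those two are the only ones that can coincide with a provider form.

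**How firmly each statement speaks**
- Section 4.5 is the only place that names year 1.
- Sections 3.1 and 6.1 imply year 1, since contact at least annually, added to provider reports that start at month 1, leaves no room for a gap of two years or more.
- Section 5.1 is the firm statement on the other side: it puts patient data after the investigators' last entry.
- Section 9.1 is weaker. It describes what the system can do beyond year 2 and does not rule out earlier use. It does introduce automatic text and email contact for that later period, while Section 6.1 describes email and text contact with no 2-year threshold.

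The real conflict is therefore Section 5.1 against Section 4.5.

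**Can other data separate reporter from time?** The claims control group in Section 8.3 has a mean follow-up of 1.70 years, shorter than the 2 years at which the reporter would change. It is therefore unlikely to show what incidence should look like across that point.

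**The case against.** The best defence is that the sequential reading is the minority one. It hangs on one adverb in Section 5.1, because Section 9.1 is an information-security section that only says what the ePRO system permits. The ePRO link sits in an app that also carries a preprocedure checklist and is offered to all enrolled patients, so nothing there blocks reporting before year 2. The design overview, the adverse-event section and the payment rule all favour overlap. This stands as an argument about what the sponsor probably meant. It does not remove the conflict: Section 5.1 defines when follow-up data are entered, and its wording could be what is built.

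One could also reconcile the text by treating the cards at years 1 and 2 as payment for information given through the provider. That would leave Sections 3.1 and 6.1 unexplained, since both describe direct patient contact as separate from the provider reports.

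Three stronger readings are tempting, and the documents do not support them.
- A reader might infer that no patient-reported data would exist before year 2. Section 6.4 has spontaneous participant-reported events recorded alongside provider reports, and participants have a toll-free number. What would be missing is scheduled, paired reporting.
- A reader might infer that sites would diverge from one another. Sections 6.1 and 9.1 describe central, automatic contact through one portal, so the risk is how that portal is set up.
- A reader might infer that contact with the patient's record lapses until year 3. Provider reports still run to year 2; only scheduled direct contact with the patient would start late.

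Finally, source-specific tables and agreement statistics may properly sit in an analysis plan that is not shown, so their absence from the protocol is no fault. The collection schedule that makes them possible belongs in the protocol.

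**Conclusion.** The inconsistency is real and should be corrected. Section 5.1, with some support from 9.1, places scheduled patient reporting after the 2-year provider report; Section 4.5 starts it at year 1, and 3.1 and 6.1 describe it as running alongside the provider reports.

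The consequence is conditional on the portal being built to Section 5.1. In that case there are 8 scheduled patient reports and no shared time point, against 10 and 2 under the other reading, and a change in reported long-term incidence after year 2 cannot be separated from the change of reporter.

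A reader might go further and put a size on the artefact, for instance an apparent fall in incidence at year 2. The documents give nothing on how completely either source reports. The shift could go either way, could differ by outcome, and is of unknown size. The case for the change rests on that being unknowable without overlap, and needs no assumed reporting rate.

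**What to change.** - Reword Section 5.1 so that scheduled patient reports run annually from year 1 to year 10, in parallel with the provider forms at years 1 and 2.
- Reword Section 9.1 so that automatic ePRO contact is not tied to the period after year 2.
- Name the year-1 start in Sections 3.1 and 6.1 too, so that all five sections agree with 4.5, and set the portal accordingly.
- Use the paired reports at years 1 and 2 to check agreement between patient and provider when interpreting incidence across year 2. The detail can go in the analysis plan.

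**Cost.** At most two extra short questionnaires per patient if the sequential schedule was intended, and none if Section 4.5 was. The annual gift card from year 1 is already planned. The change is an amendment and needs IRB approval before use under Section 10.2.

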#### 9.2 Data Access

The AGA will create a dedicated landing page for the FMT registry on its Web site, through which data access requests can be made. Interested investigators will be asked to submit a brief application including their research question(s) and requested criteria and variables. The Data Access and Publication Committee will review these requests to solely ensure that the request is appropriate and within the scope of the registry. It is anticipated that all appropriate requests for data will be granted. Once approved, data requests will be forwarded to ACI Clinical for processing. The investigators will be asked to adhere to the data sharing agreement, which includes credit to FMT Registry and the R24 as the source of the data on subsequent publications, abstracts, and other presentations. We will transmit (PHI) de-identified and aggregate data to approved applicants via

the web portal, along with appropriate documentation that describes the study methods and procedures used to collect the data, details about the codes, definitions of variables and metadata, variable field locations and other information relevant to the data use. Payment solely to cover the costs of data retrieval will be required.

Data from the eDC deployed FMT registry database will receive secure data transfers from the Mt. Sinai ePRO application per a data transfer agreement with the data processing center and Mt. Sinai to assure no PHI is transferred. Upon termination of the grant, all data and in an agreed format (SAS, ASCII) will be electronically transferred by ACI Clinical to AGA via the secure website.

## 9.3 Training

Each site will receive training on the data collection procedures and entry of data into the electronic registry. Each site will need to provide documentation of receiving and passing a training course in human subject's protections.

## 9.4 Records Retention

In accordance with federal law all records will be kept for a minimum of three years after the study has closed.

## 10 Ethics/Protection of Human Subjects

#### 10.1 Ethical Standard

The investigator will ensure that this study is conducted in full conformity with the principles set forth in The Belmont Report: Ethical Principles and Guidelines for the Protection of Human Subjects of Research, as drafted by the US National Commission for the Protection of Human Subjects of Biomedical and Behavioral Research (April 18, 1979) and codified in 45 CFR Part 46 and/or the ICH E6; 62 Federal Regulations 25691 (1997).

#### 10.2 Institutional Review Board

The protocol, informed consent form(s), recruitment materials and all participant materials will be submitted for IRB review and approval. Approval of both the protocol and the consent form must be obtained before any participant is enrolled. Any amendment to the protocol will require IRB review and approval before the changes are implemented in the study.

#### **10.3 Informed Consent Process**

Informed consent is a process that is initiated prior to the individual agreeing to participate in the study and continues throughout study participation. Extensive discussion of risks and possible benefits of study participation will be provided to participants and their families, if applicable. A consent form describing in detail the study procedures and risks will be given to the participant. Consent forms will be IRB-approved, and the participant is required to read and review the

document or have the document read to him or her. The investigator or designee will explain the research study to the participant and answer any questions that may arise. The participant will sign the informed consent document prior to any study-related assessments or procedures. Participants will be given the opportunity to discuss the study with their surrogates or think about it prior to agreeing to participate. They may withdraw consent at any time throughout the course of the study. A copy of the signed informed consent document will be given to participants for their records. The rights and welfare of the participants will be protected by emphasizing to them that the quality of their clinical care will not be adversely affected if they decline to participate in this study.

Minors may participate in the FMT registry. The minors and their legal guardians will undergo the consent process. Written consent must be provided by at least one guardian and, to the best of their ability, assent will be obtained from the minor.

The consent process will be documented in the clinical or research record.

## 10.4 Inclusion of Women, Minorities, and Children (Special Populations)

Due to the complexity of state and federal requirements governing the participation of prisoners in research, prisoner-patients shall not be approached for participation in the research registry. All other participants regardless of age, gender, race, or ethnicity will be approached to participate in this observational study. Due to the nature of observational research, AGA will monitor the progress of the study for gender and minority inclusion.

Due to the research activities, data collection, being no greater than minimum risk, children will be asked to participate. Consent for participation will be given by the child and at least one legal guardian. If the child reaches legal age, the participant will be consented again at the next patient interaction. There are only limited case reports and small studies of children who have received FMT for recurrent CDI with and without underlying IBD. To date FMT appears both safe and effective in children with recurrent or refractory CDI. Although age-specific rates and patterns of disease associated with CDI in children is poorly characterized, there has been a marked increase in CDI-associated hospitalizations from 7.24 per 10,000 in 1997, to 12.8 in 2006. Another large database analysis revealed a median age of diagnosis was 4 years and found that the 7% had one or more underlying complex chronic condition. Even with advances in medical care over the past several decades, the mortality rate in children with CDI remains stable at 4%. The experience of FMT as a primary treatment for IBD is also quite limited with mixed results. Despite limited data, FMT remains a potential therapeutic option for children with FMT and IBD. Sites that enroll minors will provide appropriate informed consent and assent per IRB protocols.

## 11 PUBLICATION POLICY

The Data Access and Publications Committee will establish requirements for publication of abstracts and research papers derived from FMT Registry data (e.g., acknowledgment of the FMT Registry and R24 support).

# **Supplement 1. Donor/Recipient Screening and FMT Technique Data Elements (characteristics to be collected once at initiation of site)**

## A. Transplant material

- Donor Stool (full spectrum)
  - Fresh
    - Time from donation to delivery
  - Frozen
    - Time from donation to freezing
  - Source
    - Directed donor (known to recipient)
      - Related
        - o Household versus non-household
      - Unrelated
        - Household versus non-household
    - Volunteer donor
  - o Age-matched: yes, no, or unknown
  - o Gender-matched: yes, no, or unknown
- Modified human stool (filtered/processed and/or enhanced)
  - o OpenBiome
    - Batch/Lot number
  - Other stool bank
  - o Specify bank
  - o Batch/Lot number
- "Commercial" stool product
  - e.g. RBX2660, SER-109
    - Batch/Lot number
  - Other
- Cultured bacterial product derived from stool
  - e.g. RePOOPulate
- Microbial consortia not derived from stool

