## 2.2 Rationale for Study Objectives Measures

## 2.2.1 To assess short-term and long-term safety

The safety of FMT is currently the greatest concern related to its use, and characterizing the safety of FMT and subsequent gut-related-microbiota products is the primary goal of the Registry. Short-term adverse events (AEs) relate primarily to the method of delivery (e.g., colonoscopy) and to acute infections or other adverse events from the donor fecal material and should be readily definable and quantifiable. Of greater concern and uncertainty is the possibility of long-term AEs. The human-to-human transfer of feces may be associated with long-term health risks to the recipient because the gut microbiota is composed of many components that have not been characterized and can change over time in ways that cannot be currently predicted. It is imperative to determine if FMT leads to unintended development of serious conditions due to the transfer of gut microbiota. In addition to infections, the possibility that gut microbiota associated with a disease phenotype (e.g., obesity, diabetes, cardiovascular disease) will be transplanted and result in chronic disease in recipients must be assessed. A prospective registry in a large sample of patients with long-term follow-up is the only practical method to achieve this aim at present.

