## 2.2.2 To characterize effectiveness of FMT and other gut related microbiota products

Current information on the efficacy of FMT in treating clinical disease is restricted to case reports, case series, and one randomized trial in recurrent CDI. Furthermore, only short-term follow-up is generally provided in these reports. Determining the short-term and long-term effectiveness in real-world practice is crucial and assessing variations in efficacy outcomes related to methodology will enable standardization and optimization of FMT practice.

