#### 3.2 Site Selection

Sites currently performing FMTs will be allowed to participate in the FMT registry. Sites may utilize any method of FMT treatment or may provide other gut-related microbiota products.

Sites selected to participate in the registry must demonstrate that all study staff have completed human subjects protection and HIPAA training prior to enrollment. Study staff must pass training on informed consent procedures, the electronic case report form (eCRF) system for data recording, and reporting procedure for unexpected events. Sites must demonstrate proper data protection procedures prior to participant enrollment. All site Principal Investigators must sign an Investigators Agreement and confirm IRB approval prior to site activity starting.

Sites will be chosen based on the following criteria: 1) FMT volume; 2) geographic location; 3) ability and willingness to comply with the requirements of registry participation; 4) have an IRB-approved protocol. In the initial phase, we will include the centers of the investigators on this proposal (n=5) and 20 centers from our listserv of 70 centers representing thought leaders in FMT with an interest in clinical investigation. To enhance representation of a geographically diverse population in the registry, centers will be related to their location in population-based regions. Using the projected number of FMTs at each center, we will enroll the number of centers in each region required to achieve a proportion of FMTs in the registry from a region to approximately mirror the proportion of the U.S. population in that region.

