## 8 Statistical Plan

## 8.1 Sample Size Determination and Power

As noted in the AHRQ's Registry User's Guide, registries are used to provide precise estimates of outcomes in real-world practice and document that potential adverse events occur at less than a pre-specified incidence with a predefined level of confidence. Plans for the FMT registry include a sample size of approximately 4,000 patients, which will provide precise estimates of incidence rates for common and rare events. For example, if the incidence of an outcome after FMT in the Registry population is 5.0%, the 95% CI will be 4.4% to 5.7%, indicating a precise estimate of treatment effect. The planned sample size will also provide high confidence in ruling out rare adverse events. If an adverse event does not occur in the planned population of 4000 patients, we will have 95% confidence that the adverse event occurs at a rate of less than one in a thousand patients undergoing FMT.

The FMT registry also will support comparative effectiveness studies focusing on different methods of delivery of FMT (e.g., colonoscopy, enema, upper GI endoscopy, nasogastric or nasointestinal tube). Statistical power for comparative effectiveness studies will depend upon the incidence of the outcome and the distribution of use of the different methods of delivering FMT. For example, assuming an outcome that occurs in one out of 1,000 FMT procedures using one delivery method, there would be 90% power to detect a difference between an incidence of 0.001 and 0.008 assuming that 2,000 patients were exposed to each of the two delivery methods. For more common outcomes, the statistical power for specific relative risk estimate is greater. For example, with 2,000 patients in each group there would be 90% power to detect a difference between two approaches for which the incidence rates of events were 3% and 5% (i.e., RR=1.67).

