To increase our ability to study unanticipated adverse events, we will include a retrospective control group of patients with recurrent CDI identified from insurance claims using Optum Insight Life Sciences, Inc data. Using these data, we can determine the incidence of relevant outcomes in a group of patients with recurrent CDI treated with antibiotics rather than FMT. The incidence of relevant outcomes in this group can be compared to the patients treated with FMT in the registry. To assure the feasibility of this approach, we have conducted a preliminary analysis of these data to identify the number of patients who will be included in the control cohort. Recurrent CDI was defined as having a physician-made diagnosis of CDI (ICD-9 008.45) treated with 3 separate courses of antibiotics with metronidazole, vancomycin, or fidaxomicin (at least one of which were vancomycin or fidaxomicin). The 3 antibiotic prescriptions had to be at least 10 days apart and the third course needed to be started within the 90 days following the CDI diagnosis. We identified 4,313 patients meeting this definition with mean follow-up of 1.70 years. The sample size should be sufficient to address questions on relatively rare outcomes. For example, at age 68 years (the median age in our control cohort), the probability of death in the next 12 months is 1.75% and the expected survival is 18.8 years (CDC lifetables). With an average follow-up time of 1.70 years, assuming equal number of subjects undergoing FMT and equal follow-up time, we would have 90% power to detect a hazard ratio of 0.77 for a difference in survival rates between FMT and antibiotic treated patients.

As mentioned above, the FMT registry also will support comparative effectiveness studies focusing on different methods of delivery of FMT. Comparative effectiveness studies rely on the ability to adequately account for differences between the treatment groups. The FMT registry will facilitate this by collecting robust data on the indications for therapy and other covariates that describe the recipients and the methods of delivery. Such data will support standard statistical methods including logistic, Cox, and other regression methods, and the development of propensity scores and risk scores for risk adjustment.

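### Supplement 1 has delivery method, product, lot, amount and schedule recorded once per site, but sections 8.1 and 8.3 plan to compare patients by delivery method

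*Protocol*

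**What the plan says.** The heading of Supplement 1, repeated in the table of contents, labels its elements "characteristics to be collected once at initiation of site". It makes no exception among parts A to F. Part A holds the transplant material, its source and the batch/lot number. Part D includes the amount delivered, part E the method of delivery and part F the schedule. Section 5.1 confirms the role of this supplement: it "details the data elements related to FMT technique including donor and recipient screening". Section 3.1 says that methodology information, including delivery, comes from each site, and it names the indication and the recipient's baseline data separately.

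The statistical sections work at patient level. Section 8.1 gives its power "assuming that 2,000 patients were exposed to each of the two delivery methods". Section 8.3 says that comparative effectiveness work, with regression and propensity scores, will be made possible by "collecting robust data on the indications for therapy and other covariates that describe the recipients and the methods of delivery". Section 3.2 sets no limit of one method per site: "Sites may utilize any method of FMT treatment or may provide other gut-related microbiota products".

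**The concern.** A comparison of delivery methods needs the method that each patient received. If the only record is one entry made when the site opened, that method is undefined or guessed wherever a site uses more than one. The entry also goes out of date. Section 3.1 expects this, writing of "Anticipating changes in therapy from current FMT to use of other gut-related microbiota products in coming years".

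Two stated aims depend on the missing link. Section 2.2.1 treats short-term adverse events as mainly a matter of how the material is delivered, and safety is the primary objective. Section 2.2.2 says that "assessing variations in efficacy outcomes related to methodology will enable standardization and optimization of FMT practice". Neither can be examined by method without a record for each recipient. A batch/lot number entered once also cannot show which lot a later recipient received, so a safety signal could not be traced to a product. An analysis plan cannot repair this afterwards, because it cannot recover an exposure that was never recorded.

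**Working it through.** **Step 1. Is the exposure recorded anywhere else?**

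| Place in protocol | Exposure data held for each patient | Method, product, lot, amount or schedule? |
|---|---|---|
| Supplement 3 | indication; treatments before FMT, including antibiotics; donor characteristics where known | no |
| Supplement 4 | CDI cure after one or after several FMTs; treatments after FMT | no |
| Supplement 5 | none (short-term outcomes, including sedation complication, bleeding, perforation) | no |
| Supplement 6 | none (long-term outcomes) | no |
| Section 5.2 and Appendix A | stool from donor and recipient; optional; planned minimum of 1,000 FMTs | no |

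The heading also clashes with items listed under it. Batch/lot number, time from donation to delivery, age and gender matching, and number of capsules used all vary between procedures.

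**Step 2. Reproduce the plan's power.** Inputs from section 8.1: n = 2,000 per method; event rates of 3% vs 5% and of 0.1% vs 0.8%. The protocol does not state the significance level, so two-sided 5% is assumed. With p̄ = (p1 + p2)/2,

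power = Φ{ [ |p1 − p2|·√n − 1.96·√(2p̄(1 − p̄)) ] / √(p1(1 − p1) + p2(1 − p2)) }

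- 3% vs 5%: (0.02 × 44.72 − 1.96 × 0.2771)/0.2768 = 1.27, so power is 89.8%.
- 0.1% vs 0.8%: power is 91.1%.

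Both agree with the stated 90%. A one-sided 5% test would give 94.3% and 95.2%, so the two-sided test is the one that matches. The arithmetic is sound, but it takes each patient's method as known.

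**Step 3. Illustration (a): method misassigned for a share e of patients in each group.** The observed rates become q1 = p1(1 − e) + p2·e and q2 = p2(1 − e) + p1·e, with n still 2,000 per group. The values of e are assumptions.

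| e | 3% vs 5% becomes | Power | 0.1% vs 0.8% becomes | Power |
|---|---|---|---|---|
| 0 | 3.0% vs 5.0% | 89.8% | 0.10% vs 0.80% | 91.1% |
| 5% | 3.1% vs 4.9% | 82.8% | 0.135% vs 0.765% | 84.6% |
| 10% | 3.2% vs 4.8% | 73.3% | 0.17% vs 0.73% | 75.4% |
| 20% | 3.4% vs 4.6% | 49.1% | 0.24% vs 0.66% | 51.0% |

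Worked line for e = 10%, 3% vs 5%: (0.016 × 44.72 − 1.96 × 0.2771)/0.2769 = 0.62, so power is 73%.

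Solving the same formula for n at 90% power and 3% vs 5% gives 2,016 per method at e = 0, 2,489 at 5%, 3,151 at 10% and 5,602 at 20%. At 10% that is about 6,300 patients in all, against 4,000 planned.

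**Step 4. Illustration (b): method undefined and those patients left out.** The shares are again assumptions.

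| Left out | n per group | 3% vs 5% | 0.1% vs 0.8% |
|---|---|---|---|
| 25% | 1,500 | 79.8% | 81.7% |
| 50% | 1,000 | 62.7% | 64.8% |

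At 1,000 per group the rare-event comparison expects about 1 vs 8 events, where the normal approximation is optimistic: Fisher's exact test gives about 56%. No allowance is made for clustering by site.

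**The case against.** The strongest reply is that the heading is a labelling slip. Several items under it make no sense once per site, and section 8.3 promises good data on delivery methods. Section 3.1 says the registry will be flexible enough to take methodological data on all product types. Section 5.1 describes the elements as ones that may be collected, and the eCRF, which is not shown, may well have a form for each procedure.

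The slip is plausible and would make the correction small. It does not remove the conflict. The flexibility clause and the permissive wording in section 5.1 do not say at what level data are captured. The promise in section 8.3 is one side of the contradiction, not its solution. Section 3.1's reference to collection from each site fits the heading, although it may only name the source. Someone building the eCRF from this text would have grounds to leave the fields out.

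Three narrower objections deserve weight:

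- The error and exclusion rates are assumed, so the power figures show sensitivity and do not predict a loss.
- An outcomes form such as Supplement 5 need not repeat the exposure. Its lack of a method field matters only because no other form for each recipient has one.
- Donor screening in part B and storage in part D depend partly on the material used. Once the material, its source and whether it was fresh or frozen (all part A) are recorded for each FMT, a site-level screening and preparation record can be linked to it, so this is workable.

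**Conclusion.** The concern holds. As written, the protocol fixes a once-per-site record for the exposure that its own comparisons need for each patient, and no other part of it supplies that record. This should be fixed.

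The stated 90% power is correct if the method is known for all 2,000 patients per group. If it is not, power for 3% vs 5% falls to between 83% and 49% for assumed misassignment of 5% to 20%, or to 80% and 63% if an assumed 25% or 50% of patients cannot be classified. The rare-event comparison behaves similarly. The size of the loss is unknown, because the documents give neither the share of sites using several methods nor an error rate. The contradiction itself does not depend on those assumptions.

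The registry's overall incidence estimates and its bound for an event never observed are not affected, since they do not use the delivery method.

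**What to change.** Reconcile the heading of Supplement 1 and section 3.1 with sections 8.1 and 8.3:

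- Limit once-per-site collection to true site policy: donor and recipient screening (parts B and C) and routine preparation practice in part D.
- State in section 5.1 that material and source, batch/lot number or donor code, amount delivered, delivery method and schedule (part A, the amount item in part D, and parts E and F) are recorded for each recipient and each FMT, including repeat FMTs.
- Correct the heading in the table of contents as well.

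If the heading is only a slip, narrowing it in both places and adding the sentence to section 5.1 is enough.

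The items are already drafted in Supplement 1. The cost is an estimated 10 to 15 short eCRF fields per procedure (our estimate, not a figure from the protocol), many skipped by branching; lot number, for example, applies only to banked or commercial product. Sites take on some entry time for each FMT. No visits or patients are added.
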